### VAS Comfort (Change)

VAS Comfort score change from pre-treatment to 5 and 10 minute post-treatment values will be analyzed separately using a linear mixed model. The model will include the following experimental design factors: treatment, sequence of treatment, region, sequence of region, period, and first-order carryover as fixed effects; subject as a random effect. Baseline characteristics such as age and gender may be included as covariates when appropriate. The covariance between residual errors for the same subject across periods will be modeled using one of the following covariance structures: Compound Symmetry (CS) or Unstructured (UN). The covariance structure that returns the lowest Akaike Information Criteria Corrected (AICC) will be selected as the structure that best fits the data. The Kenward and Roger method will be used for the calculation of denominator degrees of freedom.

The null and alternative hypothesis for superiority of anesthetized eyes compared to eyes that received the placebo with respect to VAS comfort change from pre-treatment, where  $\Delta_A - \Delta_P$  is the difference in VAS comfort change from pre-treatment between anesthesia and placebo treatments, is as follows:

$$\begin{aligned}H_0: \Delta_A - \Delta_P &\leq 0 \\H_A: \Delta_A - \Delta_P &> 0\end{aligned}$$

The hypothesis will be tested via corresponding two-sided 95% confidence interval for least-squares mean difference (anesthesia minus placebo) of VAS comfort change from pre-treatment. Superiority will be concluded if the lower limit is greater than 0 for at least one of the three ocular regions (upper lid margin, lower lid margin, or cornea).

#### 14.6. Secondary Analysis

##### VAS Comfort

The null and alternative hypothesis for superiority of eyes with the cornea anesthetized compared to with upper or lower lid margin anesthetized with respect to VAS comfort at post treatment, where  $\mu_C - \mu_L$  is the difference in VAS comfort between cornea and either lower or upper lid margins, is as follows:

$$\begin{aligned}H_0: \mu_C - \mu_L &\leq 0 \\H_A: \mu_C - \mu_L &> 0\end{aligned}$$

The hypothesis will be tested via corresponding two-sided 95% confidence interval for least-squares mean difference (cornea minus upper or lower lid margin) of VAS comfort. Superiority will be concluded if the lower limit is greater than 0 for at least one of the two differences (cornea minus upper lid margin or cornea minus lower lid margin).

The null and alternative hypothesis for equivalence of VAS comfort scores at lens removal and prior to lens application, where  $\mu_1 - \mu_2$  is the difference in VAS comfort score between lens removal and prior to lens application, is as follows:

$$\begin{aligned}H_0: |\mu_1 - \mu_2| &\geq 10 \\H_A: |\mu_1 - \mu_2| &< 10\end{aligned}$$

The hypothesis will be tested via corresponding two-sided 95% confidence interval for least-squares mean difference (lens removal minus prior to lens application) in VAS comfort score. Equivalence will be concluded if the upper limit is less than  $\delta$  and the lower limit is greater than  $-10$ .

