### Secondary Hypotheses

1. Post-treatment subjective scores of comfort (VAS scale) for eyes with the cornea anesthetized are superior to eyes with the upper or lower lid margins anesthetized.
2. Comfort change from pre-treatment for eyes with the cornea anesthetized is superior to eyes with the upper or lower lid margins anesthetized.
3. Subjective scores of comfort (VAS scale) at lens removal are equivalent to baseline levels (i.e. immediately prior to lens application in the morning) when the cornea is anesthetized. An equivalence margin of 10 points will be used.

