### 14.4. Level of Statistical Significance

All planned analysis for this study will be conducted with an overall type I error rate of 5%.

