### 14.5. Primary Analysis

#### VAS Comfort

VAS Comfort score at 5 and 10 minutes post treatment will be analyzed separately using a linear mixed model. The model will include the following experimental design factors: treatment, sequence of treatment, region, sequence of region, period, time event, and first-order carryover as fixed effects. Baseline characteristics such as age and gender may be included as covariates when appropriate. The covariance between residual errors for the same subject across periods will be modeled using one of the following covariance structures: Compound Symmetry (CS) or Unstructured (UN). The covariance structure that returns the lowest Akaike Information Criteria Corrected (AICC) will be selected as the structure that best fits the data. The Kenward and Roger method will be used for the calculation of denominator degrees of freedom.

The null and alternative hypothesis for superiority of anesthetized eyes compared to eyes that received the placebo with respect to VAS comfort at post treatment, where  $\mu_A - \mu_P$  is the difference in VAS comfort between anesthesia and placebo treatments, is as follows:

$$\begin{aligned}H_0: \mu_A - \mu_P &\leq 0 \\H_A: \mu_A - \mu_P &> 0\end{aligned}$$

The hypothesis will be tested via corresponding two-sided 95% confidence interval for least-squares mean difference (anesthesia minus placebo) of VAS comfort. Superiority will be concluded if the lower limit is greater than 0 for at least one of the three ocular regions (upper lid margin, lower lid margin, or cornea).

The null and alternative hypothesis for equivalence of VAS comfort scores at post-treatment and 5-minutes post-application, where  $\mu_1 - \mu_2$  is the difference in VAS comfort score between post-treatment and 5-minutes post-application, is as follows:

$$\begin{aligned}H_0: |\mu_1 - \mu_2| &\geq 10 \\H_A: |\mu_1 - \mu_2| &< 10\end{aligned}$$

The hypothesis will be tested via corresponding two-sided 95% confidence interval for least-squares mean difference (post treatment minus post application) in VAS comfort score. Equivalence will be concluded if the upper limit is less than 10 and the lower limit is greater than  $-10$ .

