##### VAS Comfort (Change)

The null and alternative hypothesis for superiority of eyes with the cornea anesthetized compared to with upper or lower lid margin anesthetized with respect to VAS comfort change from pre-treatment, where  $\Delta_C - \Delta_L$  is the difference in VAS comfort change from pre-treatment between cornea and either lower or upper lid margins, is as follows:

$$\begin{aligned}H_0: \Delta_C - \Delta_L &\leq 0 \\H_A: \Delta_C - \Delta_L &> 0\end{aligned}$$

The hypothesis will be tested via corresponding two-sided 95% confidence interval for least-squares mean difference (cornea minus upper or lower lid margin) of VAS comfort change

from pre-treatment. Superiority will be concluded if the lower limit is greater than 0 for at least one of the two differences (cornea minus upper lid margin or cornea minus lower lid margin).

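### Section 14.6 allows cornea-over-lid superiority from either of two unadjusted intervals, on two scales and with no deciding time, so the overall 5% in 14.4 is not delivered once both times or both scales count

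*Combined protocol and SAP*

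**What the plan says.** Section 2.3 lists two secondary superiority hypotheses. The first reads: "Post-treatment subjective scores of comfort (VAS scale) for eyes with the cornea anesthetized are superior to eyes with the upper or lower lid margins anesthetized". The second says the same of the change from pre-treatment.

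Section 14.6 gives the test for the score: "The hypothesis will be tested via corresponding two-sided 95% confidence interval for least-squares mean difference (cornea minus upper or lower lid margin"). The rule is then: "Superiority will be concluded if the lower limit is greater than 0 for at least one of the two differences". The change-score part of 14.6 repeats that rule as a separate conclusion.

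Section 14.6 specifies no model of its own, so its least-squares means presumably come from the 14.5 models. For the score, 14.5 says: "VAS Comfort score at 5 and 10 minutes post treatment will be analyzed separately using a linear mixed model". For the change: "VAS Comfort score change from pre-treatment to 5 and 10 minute post-treatment values will be analyzed separately". Section 14.6 refers only to the post-treatment score or change. It names neither 5 nor 10 minutes as deciding and does not say how the two results combine.

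On error control, 14.4 states: "All planned analysis for this study will be conducted with an overall type I error rate of 5"%. Sections 14.4 to 14.6 contain no ordering of hypotheses, gatekeeping or multiplicity adjustment. Section 14.1 calls the study a feasibility study and 14.2 calls it a pilot.

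**The concern.** A lower limit above 0 on a two-sided 95% interval is a one-sided 2.5% test. Section 14.6 gives each hypothesis two such tests at full level and accepts either. Because the deciding time is open, the hypothesis can be read out at 5 or at 10 minutes, which makes four tests per scale. With two scales there are 2 × 2 × 2 = 8 tests, each at full level.

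Two things are at stake. First, the report could cite 14.4 and present a cornea-over-lid result as error-controlled at 5% when nothing in the plan provides that. Second, the rule speaks of superiority without requiring the report to say which lid margin was beaten. A reader could then take a result against one lid as a ranking of the cornea above both.

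**Working it through.** **Inputs from the documents.** 15 completers; SD 15 or 20; intraclass correlation 0.4, 0.6 or 0.8 (14.2). Two-sided 95% intervals and the either-contrast rule (14.6). Separate models at 5 and 10 minutes (14.5).

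**Inputs assumed, because the documents give none.** Correlation of scores between regions (different days) 0.2–0.6; between 5 and 10 minutes 0.6–0.95; between pre- and post-treatment 0.2–0.8.

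**Step 1: the plan's own figures.** No error or power figure is given for the secondary hypotheses, so Table 3 serves only to check the framework. For a paired t-test, the SD of the difference is SD × √(2(1 − ICC)). At SD 15 and ICC 0.8 it is 15 × √0.4 = 9.49, the standard error is 9.49/√15 = 2.45, and a 7.5-point difference has noncentrality 7.5/2.45 = 3.06. Noncentral t on 14 df gives 0.897 at one-sided 5%, which is the tabulated value. All 18 cells of Table 3 reproduce in this way. At the two-sided 0.05 stated in 14.2 the same cell is 0.812. That mismatch is a separate matter, but the paired-t framework is evidently the plan's own.

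**Step 2: level per contrast.** The critical value is t(0.975, 14 df) = 2.145, so each contrast has a one-sided error of 2.5%.

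**Step 3: bounds.** For k tests, independence gives 1 − 0.975^k: 4.9% for k = 2, 9.6% for k = 4 and 18.3% for k = 8. The Bonferroni bounds are 5%, 10% and 20%.

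**Step 4: simulation.** Trials of 15 subjects were generated with no difference between regions (40,000–60,000 per setting), with pre-treatment, 5-minute and 10-minute scores for the anesthetized eye in each region. Cornea minus upper lid and cornea minus lower lid were tested by paired t. The two contrasts share the corneal score and so correlate at 0.5.

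| Tests counted | Number | Chance of at least one false claim | If independent |
|---|---|---|---|
| Two lids, one scale, one time | 2 | about 4.5% | 4.9% |
| Two lids, one scale, both times | 4 | 6.1–9.1% | 9.6% |
| Two lids, both scales, one time | 4 | 7.3–8.7% | 9.6% |
| Two lids, both scales, both times | 8 | 9.6–16.4% (13.0% at the middle setting) | 18.3% |

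**Step 5: effect of a remedy.** With one scale and one time named, Holm tests the better contrast at 0.025/2 = 0.0125 (critical t 2.510). The error is then at most 2 × 1.25% = 2.5%; the same simulation gives 2.3–2.4%. Requiring both lower limits above 0 gives about 0.4% when all regions are equal, and at most 2.5% when only one lid contrast is truly null.

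**The case against.** The strongest reply is that the rule quoted from 14.6, taken alone, stays under 5%. At one time on one scale the figure is about 4.5%, and the excess appears only when times or scales are added. That is correct, and it limits the point. The either-lid rule roughly doubles the 2.5% per contrast, but it does not break 14.4 by itself.

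Several stronger readings are tempting, and the documents do not support them:

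- **That success on either scale at either time is the written rule.** It is not. Score and change are separate hypotheses with separate conclusions, and the deciding time is simply unspecified. The eight-test figure describes the tests left open, not a stated criterion.
- **That the rule contradicts the hypothesis.** It does not. Section 2.3 sets the cornea against the upper or lower lid margin, and the rule matches that. The conflict is with 14.4.
- **That a high chance of passing when the cornea beats only one lid is an error rate.** With a true 10-point advantage over the upper lid, that contrast passes with probability 0.38 to 0.97 across the SD and ICC values in 14.2. This is power for a hypothesis that is true as worded. Those correlations are also tabulated for anesthetized versus placebo eyes treated at the same visit, not for regions compared across visits.
- **That the plan must require both lids, or a successful corneal anesthesia-versus-placebo result first.** Either would change the question that the sponsor chose to ask. They are design preferences.

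The pilot status and the absence of a power-based sample size also stand, and they lower the consequence. They do not remove the conflict: 14.6 states null and alternative hypotheses with a rule for concluding, and 14.4 covers everything planned.

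**Conclusion.** The point holds in this form. Section 14.4 claims an overall 5% that 14.6 has no means to deliver. Under no regional difference the chance of a false cornea-over-lid claim is about 4.5% for one scale at one time, about 6–9% for one scale at both times, and about 10–16% over all eight tests. The last is roughly two to three times the stated 5% (10/5 = 2; 16/5 = 3.2).

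The ranges depend on the assumed correlations and on paired t-tests in place of the planned mixed model with period, sequence and carryover terms. They cover the secondary superiority tests only, not the lens-removal equivalence test or the primary hypotheses. A reader might infer that 10–16% is the error of the rule as written; it is the error of a pooled family that the plan leaves open. For secondary hypotheses in a pilot this should be corrected, but it does not threaten the study.

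**What to change.** Take one of two routes.

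1. **Keep the claims.** In 14.6, name one deciding scale and one deciding time, and report the other scale and time as supportive. Adjust the two lid contrasts, for example by Holm. State any claim for the named lid only, and reserve a general statement that the cornea is superior to the lid margins for when both lower limits exceed 0. Naming the scale and time alone caps the error at 2 × 2.5% = 5%; Holm lowers it to 2.5%, the one-sided share of a two-sided 5%. Section 14.4 should also say which family its 5% covers, since an edit to 14.6 cannot control the other analyses.
2. **Make them descriptive.** Label the 14.6 superiority results descriptive with unadjusted intervals, and restrict the 14.4 statement accordingly.

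Either route takes a few sentences and no new data. The cost of the first is power. For a true 10-point difference against one lid, the first Holm step lowers power from 0.77 to 0.65 at SD 15 and ICC 0.6, and from 0.97 to 0.93 at SD 15 and ICC 0.8. The largest loss over the six SD and ICC combinations in 14.2 is 0.13 (0.59 to 0.46 at SD 15, ICC 0.4). These use the noncentral t of Step 1 with one-sided levels 0.025 and 0.0125, and assume that the 14.2 correlations carry over to comparisons between visits. The cost of the second is a less favourable 14.4 statement and no formal secondary superiority conclusion.

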#### **Secondary Objective**

To determine the effect of contact lens removal on end-of-day discomfort in symptomatic soft contact lens wearers.

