## 2.2. Endpoints

### Primary Endpoint(s)

The primary endpoint is the subjective scores of comfort (VAS scale) collected at various time points:

- Immediately prior to lens application
- 5 minutes after lens application
- 14 hours after lens application (i.e. pre-treatment)
- Immediately after lens removal prior to treatment application, only for the cornea.
- 5 minutes post-treatment
- 10 minutes post-treatment

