## **4. STUDY DESIGN AND RATIONALE**

### **4.1. Description of Study Design**

The study design is controlled, randomized, subject-masked, 3 treatment ×3 period, non-dispensing, contralateral study.

After a pre-screening assessment, eligible subjects will be invited to attend an initial visit. Subjects will be prescreened using the CLDEQ-8 questionnaire with their habitual lenses and those who are classified as symptomatic (CLDEQ-8 score of 20-37) will be scheduled for Visit 1.

At study Visit 1, subjects will be consented and screened for inclusion/exclusion criteria. If a subject is found to meet all eligibility criteria, they will be asked to attend Visit 2 which will take place on a different day. Subjects will be asked to wear their contact lenses early in the morning (at home) on the day of Visit 2 and to rate subjective comfort on a paper VAS scale immediately prior to lens application and 5 minutes post-application. They will be asked to attend the study visit having worn their habitual lenses for  $14 \pm 2$  hours. At Visit 2, one of three areas (upper lid margin, lower lid margin or cornea) will be anesthetized on one eye, whilst the fellow eye will receive a saline placebo treatment in the same location. The ocular surface region and treatment will be randomly assigned. The right eye will always be assessed first. Subjective comfort scores (VAS scale) will be collected prior to and following the treatment on each eye (5 and 10 minutes post-treatment). On the day of corneal treatment, VAS comfort scores will also be collected immediately after lens removal prior to treatment application. Subjects will be asked to return for Visit 3 on a different study day, again having worn their lenses for  $14 \pm 2$  hours and the same procedures as at Visit 2 will take place. The same procedures as for Visit 3 will be repeated for Visit 4. Visits 2-4 will be scheduled 1-14 days apart.

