Visit 2-4 (in clinic after 14 ± 2 hours of lens wear)			
Step	Procedure	Details	
2.4	Adverse Events and Concomitant Medications Review	Review any changes to the subject's medical history or concomitant medications from the previous study visit. Record any changes, and any adverse events.	
2.5	Wearing Time	Record the wearing time since application and comfortable wearing time.	
2.6	Subject Reported Ocular Symptoms	Subjects will respond to a verbal open-ended symptoms questionnaire.	
2.7	Collection of VAS scale	The investigator will collect the comfort VAS scales and will enter the scores on the database.  If subjects have not completed the VAS scales, the visit can be rescheduled to a different day for a maximum of two further occasions.	
2.8	Entrance Visual Acuity	Record the distance high contrast visual acuity to the nearest letter (OD and OS) with their habitual contact lenses.	Eurolens Research SOP #12a
2.9	Slit Lamp Biomicroscopy (white light only)	Efron Slit Lamp Classification Scale will be used to grade the findings.  If any of these slit lamp findings are Grade 3 or higher, it will be recorded as an Adverse Event.	Eurolens Research SOP #13
2.10	Subjective Lens Fit Assessment	Lens fit will be recorded according to a -2 to +2 integer scale for each of the following criteria:  Horizontal centration: -2 = Extremely Nasal -1 = Slightly Nasal 0 = Optimum +1 = Slightly Temporal +2 = Extremely Temporal  Vertical centration: -2 = Extremely Superior -1 = Slightly Superior 0 = Optimum +1 = Slightly Inferior +2 = Extremely Inferior  Coverage: -2 = Extremely Inadequate -1 = Slightly Inadequate 0 = Optimum	

		
+1 = Slightly Excessive +2 = Extremely Excessive
 
Movement -2 = Extremely Inadequate -1 = Slightly Inadequate 0 = Optimum +1 = Slightly Excessive +2 = Extremely Excessive
	
2.11	Subjective comfort	Subjective comfort scores (vertical VAS scale) will be collected for each eye.	██████████

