2.15	Left Subjective comfort	
Subjective comfort scores (vertical VAS scale) will be collected for the left eye after 5 and 10 minutes post-treatment.
 
For the cornea, the contact lens is removed and then reapplied as part of the treatment application procedures. Comfort scores will also be collected immediately (ideally within 30 seconds) after lens removal prior to treatment application.
	██████████
2.16	Contact lens removal	Contact lenses will be removed and discarded.	
2.17	Exit Slit Lamp Biomicroscopy (Visits 2-3 only)	
Efron Slit Lamp Classification Scale will be used to grade the findings.
 
Adverse events shall be documented and followed to resolution.
 
If the clearance of the fluorescein needs to be expedited, preservative-free rewetting drops or saline may be instilled.
	Eurolens Research SOP #13
2.18	Exit VA (Visits 2-3 only)	Record subjects' distance high contrast visual acuity to the nearest letter (OD and OS) with their habitual spectacle correction in place (or unaided if applicable).	Eurolens Research SOP # 12a
2.19	End of Visit (Visits 2-3)	Subject discharged and asked to return for next visit. Subjects can leave wearing spectacles or unaided as determined by the investigator.	

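### The secondary objective asks what lens removal changes, but the only planned test compares two lens-off scores and leaves out the 14-hour lens-on score

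*Combined protocol and SAP*

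**What the plan says.** Section 2.1 gives one secondary objective: "To determine the effect of contact lens removal on end-of-day discomfort in symptomatic soft contact lens wearers".

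The matching hypothesis is item 3 of the secondary hypotheses in section 2.3: "Subjective scores of comfort (VAS scale) at lens removal are equivalent to baseline levels (i.e. immediately prior to lens application in the morning"), at the cornea visit, with a 10-point margin. Section 14.6 tests it with a two-sided 95% CI for the "least-squares mean difference (lens removal minus prior to lens application) in VAS comfort score".

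Two end-of-day scores are collected at the cornea visit. The first is the lens-on score, listed in section 2.2 as "14 hours after lens application (i.e. pre-treatment") and taken at step 2.11: "Subjective comfort scores (vertical VAS scale) will be collected for each eye". The second is listed as "Immediately after lens removal prior to treatment application, only for the cornea". Steps 2.13 and 2.15 describe it: "Comfort scores will also be collected immediately (ideally within 30 seconds) after lens removal prior to treatment application".

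No analysis joins these two scores. The change analyses in sections 14.5 and 14.6 run from pre-treatment to 5 and 10 minutes after treatment. Section 14.7 plans no other exploratory analysis. Section 14.1 offers descriptive summaries and leaves further exploration to discretion.

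On the smaller point, steps 2.12 and 2.14 keep the lens in the eye for lid treatment. For the cornea, the lens is removed and re-applied. The secondary superiority contrasts are cornea minus lid, with no placebo subtraction.

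**The concern.** An effect of removal is a comparison of the same eye after and before removal. The planned test compares the evening lens-off score with the morning lens-off score, so the end-of-day discomfort named in the objective does not enter it.

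Both possible results can mislead. A finding of equivalence may mean only that there was little evening deficit to start with. A finding of non-equivalence can follow a large real gain that leaves a residual near the margin. Whether comfort returns to its morning level is a legitimate question, but a different one. As written, the sole secondary objective has no pre-specified contrast or interval.

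The smaller point concerns attribution. The corneal procedure includes taking the lens out and putting it back, while the lid procedure involves eversion and swabbing. A cornea-minus-lid difference therefore mixes anesthesia with a net handling difference of unknown size and direction. In addition, the models in section 14.5 list treatment and region but no interaction between them, although sections 2.3, 14.5 and 14.6 call for region-specific and anesthetized-eye comparisons.

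**Working it through.** **Inputs.** From section 14.2: 15 completers, SD 15 or 20, ICC 0.4, 0.6 or 0.8. From section 2.3: margin 10 (section 14.6 prints an undefined δ as the upper limit, read here as 10). From section 14.6: two-sided 95% CI. The documents give no SD or ICC for the removal contrast, so the section 14.2 grid is assumed. Deficits and removal gains are also assumptions.

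**Plan's own figure.** A paired difference has SE = SD × √(2(1 − ICC)/15) with 14 df. Integrating over the sampling distribution of the variance, a true difference of 0 at SD 15 gives 0.453/0.728/0.974 with a 90% CI. These are the Table 4 values. Under the 95% CI rule in the text the same cells are 0.237/0.536/0.933. The 95% rule is used below.

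**What the planned contrast sees.** Take a morning score of 80 and a post-removal score of 78. The planned difference is 78 − 80 = −2, whatever the 14-hour score was. If that score was 40, 60, 75 or 80, the change on removal is +38, +18, +3 or −2.

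**Chance of declaring equivalence (95% CI within ±10), ICC 0.4/0.6/0.8**

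| Residual deficit after removal | SD 15 | SD 20 |
|---|---|---|
| 3 points | 19/41/76% | 3/12/47% |
| 8 points | 5/8/12% | 1/4/8% |

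Each row holds both for a removal effect of 0 (evening deficit 3 or 8) and for a gain of 10 (evening deficit 13 or 18). With no removal effect, the rate at SD 15 is 6/10/16% for a 7.5-point evening deficit. For a 10-point deficit it is at most 2.5% in every cell at either SD.

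**Paired contrast, post-removal minus 14-hour score (noncentral t, 0.025 one-sided)**

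| | SD 15 | SD 20 |
|---|---|---|
| CI above 0, no effect | 2.5% | 2.5% |
| CI above 0, 10-point gain | 59/77/97% | 38/52/81% |
| 95% half-width, one score per subject | 9.1/7.4/5.3 | 12.1/9.9/7.0 |
| 95% half-width, two eyes averaged, at best | 6.4/5.3/3.7 | 8.6/7.0/5.0 |

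Half-width = 2.145 × SE. For SD 15 and ICC 0.6, SE = 15 × √(0.8/15) = 3.46, so the half-width is 7.4. The two-eye row uses SE = SD × √((1 − ICC)/15), which requires the changes in the two eyes to be independent.

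A simulation at SD 15 (200,000 trials per cell) agrees. Deficit 3 with no effect gave equivalence in 19.1/40.9/75.5% and a paired CI above 0 in 2.5/2.4/2.5%. Deficit 13 with a 10-point gain gave 19.2/40.8/75.4% and 59.4/76.4/96.6%.

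**Cornea versus lid.** Suppose a 7.5-point corneal advantage exists in anesthetized eyes only. Fitted exactly as listed, the region effect averages over anesthetized and saline eyes and estimates (7.5 + 0)/2 = 3.75. Power at SD 15 is then 21/30/52%, against 38/52/81% for the anesthetized-eye contrast.

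The placebo-corrected contrast has SE = SD × √(4(1 − ICC)/15), which is √2 times the raw SE (41% higher). Its half-width is 12.9/10.5/7.4 (SD 15) or 17.2/14.0/9.9 (SD 20). Power at 7.5 points is 21/30/52% or 14/19/33%.

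**The case against.** Item 3 of the secondary hypotheses can be read as the sponsor's chosen way to study removal: once the lens is out, is comfort back to its lens-free morning level? Section 14.1 promises descriptive summaries of efficacy variables as appropriate, and the difference of the two tabulated means is the mean change. The primary model also names a time-event factor, which might include the 14-hour level. Any equivalence test depends only on its own contrast, so the identical rates above follow by construction. False reassurance also needs a small evening deficit, and the study recruits symptomatic wearers. The paired change is itself an uncontrolled before/after comparison, rated straight after an event the subject cannot be masked to. Finally, this is a pilot.

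Part of this stands. The before/after limitation is real, and the documents do not show that a small deficit is likely. But two tabulated means give no paired interval, the time-event levels are not listed, and discretionary exploration does not pre-specify an estimate for a named objective. Pilot or not, sections 2.3 and 14.6 set formal hypotheses and decision rules. The opposite error, a real gain read as non-equivalence, does not need a small deficit.

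On the smaller point, the decision rules require region-specific differences, so the factor list may well be shorthand. If so, the interaction only needs to be stated, and the 3.75-point figure does not arise. Steps 2.13 and 2.15 also suggest that both eyes' lenses are removed at the cornea visit.

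**Conclusion.** The concern holds. Followed exactly, the plan can return either answer on equivalence without showing what removal changed. That reading needs no assumed values. The percentages rest on the section 14.2 SD and ICC grid, one common ICC, 15 completers, and assumed deficits and gains.

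The smaller point is a matter of attribution and model statement. No handling effect size is claimed. The primary anesthesia-minus-placebo comparison within a region is unaffected if both eyes are handled alike.

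**What to change.** **Main.** In section 14.6, name the analysis of the secondary objective as the post-removal score minus the 14-hour pre-treatment score of the same eye at the cornea visit, averaged over the two eyes within subject, with a 95% CI. Report it as an uncontrolled before/after change. Section 4.1 says "The right eye will always be assessed first", so the left eye's 14-hour score is at least 10 minutes older when its lens comes out; add a right-eye-only sensitivity analysis. Keep the equivalence test as a separate statement on return to baseline.

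**Smaller point.** State a treatment-by-region term in both section 14.5 models. Report (anesthesia minus placebo at the cornea) minus (the same at the lid), for score and for change, with 95% CIs. Treat this as descriptive support only, because it is imprecise. State its assumptions: the saline eye is handled equally and the handling effect is additive. An anesthetized cornea may feel re-application differently from a saline-treated one.

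Steps 2.12 to 2.15 and SOP #54 differ on lens handling. The SOP ends the corneal contact-lens method and the lid procedure with lens removal. These passages must be reconciled, including whether the saline eye's lens is also removed and re-applied. If it is not, only one eye contributes to the removal contrast and the one-score half-widths apply.

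**Cost.** No new data: one pre-specified contrast with its sensitivity analysis, one model term and one descriptive contrast.
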